- a Background: There is an urgent need for effective and safe chemoprophylaxis against novel Corona Virus Disease of 2019 (COVID-19) due to Severe Acute Respiratory Syndrome- Corona Virus-2 (SARS CoV-2). There is no drug or any vaccine available. Based on extrapolation of antiviral effect and down regulation of aberrant immune response demonstrated in laboratory experimental studies (including SARS virus and recently some data on SARS-CoV-2) and very sparse clinical data, Hydroxychloroquine (HCQ) was given to several high risk participants such as health careproviders as per the regimen contained in the ICMR advisory: 400 mg twice daily on day one and to be followed by 400 mg weekly for seven weeks [The entire advisory is enclosed with this protocol (Appendix S, pages 109-111)]. The pandemic is likely to last longer. Over short-term use, drug toxicity may not be much of a concern but long-term use of HCQ will need diligent monitoring of several adverse effects. Several clinical research studies have been initiated globally to investigate the therapeutic role of HCQ in COVID-19. Other options for chemoprophylaxis include Ashwagandha; an Ayurveda 'Rasayana' is popularly used since ancient times to build up the immunity which is central to combat infectious illness like COVID-19. Several experimental studies have also demonstrated convincingly the immune enhancing and modulating properties of Ashwagandha. There are other health benefit also- anabolic, anti-oxidant, tissue protective. A recent Indian experimental study has conclusively demonstrated that Ashwagandha can effectively interfere with the binding of SARS-CoV-2 to the host cell receptor (ACE 2) but requires further validation. Ashwagandha has been clinically evaluated in auto-immune disorders such as rheumatoid arthritis (RA). The investigators ([name]) have reported equivalent efficacy of an Ashwagandha formulation and HCQ for management of Rheumatoid Arthritis in a controlled clinically study of RA of 6 months duration (38). Therefore, Ashwagandha is likely to show clinical benefit through its predominant effect on the immune system in case of COVID-19.
- **b.** Study title: Ashwagandha for the Prophylaxis against SARS-CoV-2 Infection: A Randomized Hydroxychloroquine Controlled Clinical Trial in Health Care Providers
- **c. Objective:** This research project is a randomized control trial (RCT), which aims to study the efficacy; safety and other health benefits of Ashwagandha in the prophylaxis against COVID-19 in High Risk Population (HRP) in comparison with HCQ.
- **d** The investigational product: The investigational product is Ashwagandha (an aqueous extract of *Withania somnifera*) and this will be compared to HCQ.
 - e. Study duration: The study duration will be of 12 weeks.
- **f** Study design: Consenting eligible HCP will be randomized to a prospective, open label, two arms, parallel efficacy multi-centric study with an equivalence design (sample size = 400 participants). The study design is as per Zelen Model wherein the participants are permitted to exercise their choice of the study drug. The HCP will be selected if they are naïve for prior HCQ use and are actively involved in the management of COVID-19 cases. This is an equivalence design study (equivalence margin of difference 15% with HCQ, 80% power, alpha 0.05 or less). Participants in the HCQ arm will take HCQ for 7 weeks only but will be monitored and evaluated up to study completion at week 12. However, participants in the Ashwagandha arm will continue to take the drug for the total duration of 12 weeks but will be monitored at 7th week, similar to those on HCQ.

Figure 1: Study Design and timelines

Screening of * High Risk Population & Obtain Study Consent (Exclude SARS-CoV-2 infection/COVID, Verify Eligibility Criteria) *At Risk: HCP, Contacts of COVID-19 cases, Certain Work Class

Enrol Study Participants

HCQS naïve, Managing COVID- 19 cases: Randomised, 2 Arm Interventional (HCQS or Ashwagandha) Study

Time Points*	Clinical Assess	Laboratory Assess
Baseline	Clinical Examination including Ayurvedic analysis, Assess QOL with WHO Qs, Assess HR- BHF, Initiate Study documents	Diagnostic (RT-PCR), Serology (IgM, IgG), Routine Body Profile, Selected Cytokine Assay
Week 4	Telephonic Check for COVID Symptoms, Self- Assess Qs, Assess Drug safety	Diagnostic (RT-PCR), Serology (IgM, IgG)
Week 8	Telephonic Check for COVID Symptoms, Self- Assess Qs, Assess Drug Safety	Diagnostic (RT-PCR), Serology (IgM, IgG)
Week 12	Clinical Examine including Ayurvedic, Completion Study Report, Assess QOL with WHO Qs, Assess HR-BHF, Outcomes, Assess Drug Safety	Diagnostic (RT-PCR), Serology (IgM, IgG), Routine Body Profile, Selected Cytokine Assay

^{*}Further Assessment Points: Daily Mobile App based feedback of any COVID-19 Symptoms or drug related side effects;

Participants will also be checked any time in case of suspected COVID-19 symptoms

NOTE: The total study period is 12 weeks; HCQS and Ashwagandha are Study Intervention Drugs; HCQ will be given weekly for only 7 weeks (ICMR Advisory) but participants followed till study completion; Participants will be monitored and followed using a common scheme shown above; Primary Efficacy Measure: Proportion of participants free from SARS-CoV-2 infection and/or COVID-19 on Study Completion; Participant testing positive for SARS-CoV-2 and/or developing COVID-19 will be withdrawn and referred to COVID-19 medical facility; Both Ayurvedic and Allopathic Physicians will examine and monitor participants; Cytokine Assay in only selected participants; HCP: Health Care Provider; HCQ: Hydroxychloroquine; Qs: Questionnaire; HR-HBF: Health Related habits, behaviour and Fitness. (Detailed methodsare described in Appendix A to R)

g Study Population: Voluntary study participants will be selected from high risk population for COVID-19. This population includes HCP actively participating in the management of COVID-19 cases.

Eligibility Criteria:

Inclusion Criteria:

- Participants of either sex, 20 to 69 years of age
- Participants tested negative for COVID-19 by nose and throat swab using RT PCR technique
- HCQS naïve participants
- Willing to come for regular follow up visits
- Written Informed Consent

Exclusion Criteria:

1.	Participants with hypersensitivity or Intolerance and contraindications (psoriasis, porphyria and Glucose-6-Phosphate Dehydrogenase deficiency)
2	Pregnant women, lactating women and women of child bearing potential
3.	Participants with known allergy or contraindication to Ashwagandha
4	Have any Chronic, Severe, Unstable, Uncontrolled medical disease such as Diabetes, Hypertension, Cardiac disorders, liver, kidney disorders and lung disorders or other disease of concern which may put the participant at increased risk during the study
5	History of having received any investigational drug in the preceding one month.
6	Prolonged concurrent intake of any drug that is known to prolong QT interval on the ECG as per physician discretion and these drugs include anti-arrhythmic drugs, quinidine, chlorpromazine, haloperidol, olanzapine, thioridazine, fluoxetine, antibiotics belonging to quinolone and macrolide family, antibiotics, fenfluramine and other appetite suppressants, Beta-2 agonists, terfenadine and other antihistaminic drugs, liquorice and potassium lowering drugs
7	History of taking any kind of Ayurvedic formulation or any other form of CAM (Complimentary Alternative Medicine) therapy in the preceding 2 months
8	Unwilling to come for regular follow-up for the entire duration of the study.
9	Non – co-operative attitude of the participant
10	Any condition that, in the opinion of the investigator, does not justify the participant's inclusion in the study.

h Sample size: 400 (randomized sample size)

i Treatment and Follow up Monitoring Schedule:

This will be common to both the study arms

Visit - 1: Baseline Visit

Visit - 2: Week 4 Visit

Visit - 3: Week 8 visit

Visit - 4: Week 12 visit

Participants will be under the combined care of Modern medicine physician and Ayurvedic physician. The details of the procedures and investigations carried out at each visit are as mentioned in the Schedule of Events (Appendix A)

i. Concomitant medication:

Medication prescribed for other co-existent disease will continue under medical supervision which will be recorded in the case record form (CRF).

k Efficacy criteria:

The primary efficacy measure will be as follows:
(i)Proportion of SARS-CoV-2 infection* free participants
on completion of study (ii)Proportion of participants
contracting COVID-19 during the study period
The secondary measures of efficacy and safety will include proportion of
participants developing COVID-19, drug related adverse event, drug
tolerability, General Health Related Questionnaire (behavior, habit and
fitness/ HR-BHF), Quality of life (WHO QOL Brief), Ayurveda
measures, Immune Status (serology for specific anti SARS-CoV-2 IgM
and IgG antibodies)

- *The diagnosis of COVID-19 will be confirmed by a real time RT-PCR based diagnostic test on nose/mouth swab
- 1 Safety criteria: All adverse events occurring during the study will be recorded and monitored as per GCP-ICH guidelines. Safety would also be assessed in case of all withdrawals.
 - m. Laboratory investigations: These are common to the both the study arms
 •Haemogram, Platelet count, Total leukocyte differential count, Hemoglobin and ESR.
 - ·Liver function test Serum Bilirubin, ALT, AST, Alkaline phosphatase,
 - •Kidney Function Test (Serum creatinine, Blood Urea Nitrogen)
 - •Lipid profile (Total cholesterol, HDL cholesterol, LDL cholesterol, Triglycerides, VLDL)
 - Blood Sugar Level
 - •Urine Routine
 - •C-Reactive protein
 - •Selected Cytokines: Gamma Interferon, tumor necrosis factor (TNF-alpha and beta), Interleukin (IL) IL-6, IL2, IL-10, IL-17, Monocyte Chemotactic Protein-1
 - •Nasal and throat swab for specific test for COVID-19 based on real time RT-PCR
 - •Serum for IgG and IgM for COVID-19

n Statistical statement:

The design considers equivalence between HCQ and the Ashwagandha arm with a-priori margin set at 7.5% two sided. Standard statistical tests, parametric and non-parametric, will be used for analysis (both intention to treat and per protocol); significance p < 0.05 two sided.

a Regulatory clearances:

The protocol will be submitted for all regulatory and other relevant approvals including that of the ethics committee prior to beginning the clinical component of the study.

p Funding agency:

COVID-19/AYUSH-CSIR 2020/Version MOA-Approved dated 13 May 2020, is an undertaking of AYUSH-CSIR, Government of India, and is being directly funded by Government of India.

q Guidelines:

The study will be conducted in accordance with the updated principles of Good Clinical Practice (GCP) described by WHO and the current version of the Declaration of Helsinki, Indian Council of Medical Research (ICMR) Ethical Guidelines for Biomedical Research on Human participants -2017, and Ministry of AYUSH/ Central Council for Research in Ayurvedic Sciences (CCRAS) guidelines on the subject (2018) including archiving of essential documents.

STUDY PROCEDURES/TIMELINES AND EVENTS SCHEDULE

The overview is shown in Table 1.

Baseline Visit: (Visit 1): Exclusion criteria

Participants who meet the criteria for selection, must have the following procedures completed during this visit prior to study entry.

Visit 1 (Baseline)

0	Providing with Participant Information Fact Sheet (Appendix C) for thorough study.
0	Signing of Informed Consent. (Appendix B)
0	Complete medical examination form: medical history, physical examination, vital signs (BP, Pulse, Respiration rate and Weight), comorbidity, medication history.
0	Record Baseline Symptoms
0	Ayurvedic evaluation.
0	Quality of life as assessed by WHO-QOL Brief and Health Related- Behavior Habit Fitness questionnaire
23.25	Laboratory work up- general health and cytokines (anti-TNF, IL 6, gamma interferon, IL 13)
0	Laboratory work up-diagnostic for COVID-19 (nose/throat swab and serology)
0	Dispense study medication and begin medication log entry
0	Schedule return visit in 4 weeks

Visit 2 (Week 4):

0	Complete Follow Up Assessment

0	Laboratory work up-diagnostic for COVID-19 (nose/throat swab and serology)
0	Monitor Adverse Events
0	Check study participant pocket diary
0	Dispense study medication and update medication log
0	Schedule return visit in 4 weeks.

Visit 3 (Week 8):

0	Complete Follow Up Assessment
0	Laboratory work up-diagnostic for COVID-19 (nose/throat swab and serology)
0	Monitor Adverse Events
0	Check study participant pocket diary
0	Dispense study medication and update medication log
0	Schedule return visit in 4 weeks.

Visit 4 (Week 12):

0	Complete Follow Up Assessment
0	Complete medical evaluation
0	Ayurvedic evaluation
0	Complete questionnaire for Quality of life – WHO QOL and Health Related Behaviour Habit and Fitness questionnaire
0	Laboratory work up-general health and cytokines (anti-TNF, IL 6, gamma interferon, IL 13)
0	Laboratory work up-diagnostic for COVID-19 (nose/throat swab and serology)
0	Complete Follow Up Assessment
0	Update medication log (record any unused study medication)
0	Check study participant pocket diary
0	Monitor Adverse Events
THE PARTY	Record final outcome

Prophylactic study sites

- 1. RRAP Central Ayurveda Research Institute for Cancer (CCRAS), [name].
- 2. Dept. of Pharmacology and Therapeutics, , GS Medical College & KEM Hospital, Parel, Mumbai.
- 3. TN Medical College and Nair Hospital, Mumbai Central, Mumbai.
- 4. Post graduate Institute of Medical Education & Research, Chandigarh.
- 5. ESI Hospital, [name]
- 6. King George Medical University, Lucknow.
- 7. Banaras Hindu University, Varanasi

Adjunct Treatment study sites

- 1. Symbiosis University Hospital & Research Centre, Symbiosis Inter
- 2. All India Institute of Ayurveda (AIIA), [name].
- 3. RRAP Central Ayurveda Research Institute for Cancer (CCRAS), [name]
- 4. D Y Patil University school of Medicine & Hospital, Nerul, Navi Mumbai.
- 5. Medanta Institute of Education and Research, Gurgaon.

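### The prophylaxis protocol consents people before randomising them, yet calls the design a Zelen model with free choice of drug; any switching would shrink the intention-to-treat difference and favour a false equivalence claim.

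*Protocol*

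**What the plan says.** All references are to the prophylaxis study in the protocol.

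- **Order of consent and randomisation.** Section f (Study design) opens: "Consenting eligible HCP will be randomized to a prospective, open label, two arms, parallel efficacy multi-centric study with an equivalence design". Figure 1 places consent in the screening box, ahead of enrolment and randomisation: "Obtain Study Consent (Exclude SARS-CoV-2 infection/COVID, Verify Eligibility Criteria". The inclusion criteria list "Written Informed Consent", and the Visit 1 list has the form signed before study entry.
- **Choice of drug.** Section f continues: "The study design is as per Zelen Model wherein the participants are permitted to exercise their choice of the study drug".
- **Aim and margin.** Section f gives "equivalence margin of difference 15% with HCQ, 80% power, alpha 0.05 or less". Section n (Statistical statement) gives "with a-priori margin set at 7.5% two sided".
- **Analysis.** Section n: "Standard statistical tests, parametric and non-parametric, will be used for analysis (both intention to treat and per protocol); significance p < 0.05 two sided". It does not say which analysis set decides equivalence, or whether both must agree.

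The text at hand sets no limit on the choice, states no expected share of participants taking the other drug, and gives no rule for analysing them.

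**The concern.** The defining feature of a Zelen design is that people are randomised first and consent is sought afterwards for the arm they were given. Crossing to the other arm is the price paid for that order. Here consent comes first, so the reason for the design is absent and only its price is left.

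That price matters more in an equivalence trial than in a superiority trial. When some people in each arm take the other arm's drug, the arms look more alike under intention to treat. In a superiority trial this is conservative. In an equivalence trial it moves the result towards the conclusion the trial hopes to reach.

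The usual counterweight is a per-protocol analysis. When leaving the allocated drug is the participant's own choice, made by health workers who know both drugs, dropping the switchers leaves a self-selected comparison whose bias could go either way. At stake is whether an equivalence claim would mean what it says.

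**Working it through.** **1. The plan's own figure.** The total is 400, but no infection rate is given, so it cannot be reproduced. For two one-sided tests (TOST) with 80% power and true difference 0, n per arm = 2p(1−p)(z(1−a) + z(0.90))² / margin².

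- 15-point margin, one-sided a = 0.05: the largest total, at p = 50%, is 382.
- 15-point margin, a = 0.025: 400 corresponds to p of about 31%.
- 7.5-point margin: 400 corresponds to p of about 7.1% (a = 0.05) or 5.7% (a = 0.025).

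So one cannot tell whether 400 contains any allowance for switching; none is stated.

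**2. Inputs for the dilution check.**

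- From the protocol: total 400; margins 15 and 7.5 points; binary primary endpoint.
- Assumed: 1:1 allocation (200 per arm); HCQ-arm infection rate 5%, 10% or 20%; switching share c.
- Either a 90% interval (one-sided 0.05 twice) or a 95% interval, because the protocol's alpha wording allows both.
- True infection rate on Ashwagandha = HCQ rate + margin, so every equivalence claim is false.

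**3. Formula.** With shares cH and cA taking the other drug, the intention-to-treat difference = true difference × (1 − cH − cA). For c in both arms, a true 15 points becomes 12 at c = 10% and 9 at c = 20%.

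**4. One case by hand.** 15-point margin, HCQ rate 10%, c = 10% in both arms, 90% interval.

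- Intention-to-treat rates: 0.9 × 0.10 + 0.1 × 0.25 = 0.115, and 0.9 × 0.25 + 0.1 × 0.10 = 0.235.
- Standard error: √[(0.115 × 0.885 + 0.235 × 0.765)/200] = 0.0375.
- The interval lies inside the margin if the observed difference is below 0.15 − 1.645 × 0.0375 = 0.088.
- Probability: Φ((0.088 − 0.120)/0.0375) = Φ(−0.85), about 0.20. Exact binomial enumeration gives 0.203.

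**5. Exact enumeration.** Probability (%) that the Wald interval falls inside the margin. Each cell is for HCQ rates of 5 / 10 / 20%.

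| Margin, interval | No switching | 10% both arms | 20% both arms | 20% out of Ashwagandha only |
|---|---|---|---|---|
| 15, 90% | 5.6 / 5.2 / 5.0 | 24.5 / 20.3 / 16.8 | 57.6 / 48.2 / 38.7 | 26.6 / 21.3 / 17.1 |
| 15, 95% | 3.0 / 2.7 / 2.5 | 16.2 / 12.7 / 10.0 | 45.8 / 36.0 / 27.2 | 17.8 / 13.5 / 10.3 |
| 7.5, 90% | 5.7 / 5.0 / 2.2 | 14.5 / 10.7 / 3.8 | 29.1 / 19.3 / 5.9 | 15.2 / 11.2 / 4.3 |
| 7.5, 95% | 3.0 / 2.0 / 0.0 | 8.5 / 4.5 / 0.0 | 18.9 / 8.4 / 0.0 | 9.1 / 5.2 / 0.0 |

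The zeros in the last row have a simple cause. At an HCQ rate of 20% without switching, the standard error is √[(0.20 × 0.80 + 0.275 × 0.725)/200] = 0.0424. The 95% half-width is then 1.96 × 0.0424 = 0.083, wider than the margin, so equivalence can hardly ever be concluded.

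**The case against.** The strongest reply is that the size is unknown. The protocol gives no switching share; if nobody switches, there is no dilution. How the choice operates may be described in appendices that are not shown. The figures also depend on settings: a 95% interval, one-way switching or a high infection rate all reduce them. This stands. It is why the results are given as ranges and why, for the 7.5-point margin, the effect can be negligible.

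A second reply is that section n already pairs intention to treat with per protocol, as is usual for equivalence. This stands in part. The pairing gives some protection, but section n does not require the two to agree, and chosen non-adherence is the case in which per protocol is weakest.

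Three stronger readings are tempting and are not supported:

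- **That the error rate is certainly above 5%.** It depends on switching that may not occur. With the 7.5-point margin and a 95% interval it stays below 5% at 10% switching in both arms for HCQ rates of 10% and 20%.
- **That neither planned analysis can be relied on.** Self-selection can bias per protocol in either direction; that does not make it worthless. No as-treated analysis is planned.
- **That the arms are not randomised because people pick their drug.** The sentence does not say whether choice precedes or follows allocation, but the sentence before it says that participants are randomised.

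**Conclusion.** The point holds as a contradiction with a known direction of bias and an uncertain size. The Zelen label does not fit a trial that takes consent first, and the stated freedom to choose works towards equivalence under intention to treat whenever the drugs differ and some participants switch. A later analysis plan cannot fully undo this, because the protocol itself authorises the choice.

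Under the assumptions above:

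- **15-point margin:** the risk of false equivalence goes from about 5-6% to 17-25% at 10% and 39-58% at 20% two-way switching (90% interval), or from about 3% to 10-16% and 27-46% (95% interval). With 20% switching out of the Ashwagandha arm only, it is 17-27% or 10-18%.
- **7.5-point margin:** at 20% two-way switching it is 6-29% (90%) or 0-19% (95%). At a 20% infection rate there is little or no inflation.

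Confidence is high in the contradiction and the direction, and moderate in the size. The two margins also need reconciling, which is a separate matter.

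**What to change.** Delete the Zelen sentence and the choice of drug from section f. State ordinary individual randomisation after consent, and add to the eligibility criteria that the participant is willing to take either study drug. The cost is an amendment to the design text, one added criterion and matching consent wording. Some people with a strong preference will decline; the protocol gives no basis for saying how many.

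If choice is kept, say when it is exercised and record every switch. Claim equivalence only if the intention-to-treat interval and a complier-average (instrumental-variable) interval both lie inside the margin.

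That fallback lowers power, and the protocol should say so. As an approximation, the complier-average interval lies inside the margin when the intention-to-treat interval lies inside margin × (1 − 2c). With true difference 0, 200 per arm, a 90% interval and the 7.5-point margin, power at 0, 10 and 20% two-way switching is about 92, 74 and 35% at a 5% infection rate, and 62, 28 and 1% at 10%. With the 15-point margin the loss is small at a 5% rate (about 98% power remains at 20% switching), but at a 20% rate power falls from about 96% to 83% and 46%.

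### The prophylaxis primary endpoint is one composite in the Figure 1 note but two unlinked measures in section k, one of them also listed as secondary, and the equivalence margin is tied to neither

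*Protocol*

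**What the plan says.** Everything here is in the prophylaxis synopsis.

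- **Figure 1 note (section f).** One composite: "Primary Efficacy Measure: Proportion of participants free from SARS-CoV-2 infection and/or COVID-19 on Study Completion". The same note names a positive test and the development of COVID-19 as separate triggers for leaving the study: "Participant testing positive for SARS-CoV-2 and/or developing COVID-19 will be withdrawn".
- **Section k, primary.** The lead-in is singular but two items follow. The first is "i)Proportion of SARS-CoV-2 infection* free participants", assessed on completion. The second is the proportion "contracting COVID-19 during the study period". No rule combines or ranks them.
- **Section k, secondary.** The next sentence begins "The secondary measures of efficacy and safety will include proportion of" and goes on to participants developing COVID-19, which repeats the second primary item.
- **Section k, footnote.** The only case definition shown hangs on the word infection but speaks of the disease: "The diagnosis of COVID-19 will be confirmed by a real time RT-PCR based diagnostic test on nose/mouth swab". There is no symptom criterion.
- **Margin and power.** Section f gives a 15% margin, 80% power and alpha of 0.05 or less. Section n gives a 7.5% two-sided margin and two-sided significance at 0.05. Neither names the measure concerned. Section h gives 400 randomised.

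**The concern.** An equivalence conclusion rests on one proportion per arm compared with one margin. Here the proportion is described in two ways, with two time references (on completion, and during the study), and one component is both primary and secondary.

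This has practical consequences because Figure 1 schedules RT-PCR for everyone at weeks 4, 8 and 12, so infections without symptoms will be found. If COVID-19 means illness, such a participant is an event for the first measure and not for the second. The margin is an absolute difference, and a rarer event has a smaller standard error and usually a smaller absolute difference, so the rarer measure passes more readily. The trial is open label, so a choice of primary left open could be made with knowledge of the results by arm.

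**Working it through.** **The plan's own figure.** The total of 400 cannot be reproduced, because the synopsis states no event rate, dropout or allocation ratio. It can be solved backwards. For two one-sided tests with no true difference, n per arm = 2p(1-p)(z[1-a] + z[1-b/2])² / m². With n = 200 (equal allocation assumed) and 80% power (z[1-b/2] = 1.282):

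| Margin m | One-sided a | (sum of z)² | Event rate implied by 400 |
|---|---|---|---|
| 7.5 points | 0.05 | (1.645 + 1.282)² | about 7.1% |
| 7.5 points | 0.025 | (1.960 + 1.282)² | about 5.7% |
| 15 points | 0.025 | (1.960 + 1.282)² | about 31% |
| 15 points | 0.05 | (1.645 + 1.282)² | none; at most 382 needed, at p = 0.5 |

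So whether 400 suffices depends on how common the primary event is, and hence on which measure is meant.

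**Reading A: COVID-19 is the RT-PCR result over the same period.** The composite and the first measure are then the same variable, and the second is its complement. Replacing p by 1-p reverses the sign of the difference and leaves the standard error unchanged, and the margin is symmetric, so the verdict cannot change. All 201 × 201 pairs of counts at 200 per arm were checked at both margins with 90% and 95% intervals: 0 disagreements.

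**Reading B: COVID-19 is symptomatic, RT-PCR-confirmed disease.** It is then a subset of infections. The composite reduces to the first measure, and only the second can differ. Counts, symptomatic share and 200 per arm are assumptions. The interval is d ± z × SE, with SE = √[p₁(1-p₁)/200 + p₂(1-p₂)/200].

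| Events per 200 | d (points) | SE (points) | 90% CI | 95% CI | 7.5 points | 15 points |
|---|---|---|---|---|---|---|
| 20 v 10 infected | 5.0 | 2.62 | 0.7 to 9.3 | -0.1 to 10.1 | fail | pass |
| 10 v 5 symptomatic | 2.5 | 1.90 | -0.6 to 5.6 | -1.2 to 6.2 | pass | pass |
| 60 v 44 infected | 8.0 | 4.37 | 0.8 to 15.2 | -0.6 to 16.6 | fail | fail |
| 24 v 18 symptomatic | 3.0 | 3.06 | -2.0 to 8.0 | -3.0 to 9.0 | fail | pass |

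The first pair splits at 7.5 points but not at 15. The second splits at 15 points. The verdicts are the same with either interval.

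**How often the verdicts differ under Reading B.** A simulation used 200,000 runs per scenario, equal true rates, 200 per arm and 95% intervals, with infection rates of 5% to 30% and symptomatic shares of 30% to 70% (all assumed). The two verdicts differed in 0.3% to 76% of trials at 7.5 points and in 0% to 19% at 15 points. At 10% infected, half symptomatic and 7.5 points, 42% passed on infection, 86% on symptomatic disease and 40% on both; 48% were discordant.

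**The case against.** Several limits stand.

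- A reader might infer that because the footnote makes COVID-19 an RT-PCR result, the same data can both pass and fail. It is the other way round: if the two are the same test result over the same period, they cannot disagree (Reading A). The footnote says confirmed by RT-PCR, which fits Reading A but also fits a confirmed subset of infections. Disagreement needs that subset reading, or a difference in time window or in the counting of withdrawn positives.
- A reader might take the composite's wording to include clinically diagnosed, swab-negative illness, a larger event count. The footnote does not support that: without a positive RT-PCR the diagnosis is unconfirmed, and nothing says unconfirmed illness counts.
- A reader might infer that success on either section k item suffices. The text does not say so; its lead-in is singular. The defect is that no rule is given.
- The 80% power is stated alongside the 15% margin, and at 15 points the 20 versus 10 example no longer splits. Splits remain possible there but are rarer. The two margins are a separate inconsistency, and 15% may be the full width of plus or minus 7.5 points.
- The text refers to Appendices A to R, which are not shown and may hold a case definition. That would settle the reading of COVID-19, but it would not remove the mismatch between one primary and two, or the primary-secondary duplication.

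**Conclusion.** The point holds as an inconsistency in the primary definition. One composite stands against two measures, the time references differ, nothing links the two items, and the COVID-19 proportion is both primary and secondary within section k. The margin and power refer to no named measure. These facts need no assumptions.

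The consequence is conditional. On one reading the second primary is redundant and harmless to the verdict. On the other it is a rarer and easier test that can contradict the first, at 7.5 points and, less often, at 15. The sizes shown rest on assumed event rates, symptomatic shares and 200 per arm; the documents give none of these. The definition should be settled before outcomes are compared by arm.

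**What to change.** State the same single primary in the Figure 1 note and in section k. One suitable choice is the cumulative proportion with at least one positive SARS-CoV-2 RT-PCR from randomisation to week 12, with or without symptoms, counting participants withdrawn after a positive test as events. This settles the case definition, the time window and the counting of withdrawn positives together.

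Then:

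- Tie the margin, alpha and power to that measure by name.
- Delete COVID-19 as the second primary item and keep it as the secondary that section k already lists, defined as symptomatic and RT-PCR-confirmed.
- If both are kept as primary, state that both must meet the margin, and accept the loss of power (40% for both against 42% and 86% singly in the simulated example).
- Reconcile the wording of the withdrawal sentence in the Figure 1 note with the chosen case definition, without changing clinical management.

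The cost is protocol wording; the swabs are already scheduled. The downside is that equivalence can no longer be claimed on the rarer measure alone.

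### Prophylaxis trial: drug-related adverse events share one 12-week window although HCQ is taken for 7 weeks and Ashwagandha for 12, so 12-week totals do not measure relative tolerability unless exposure is stated

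*Protocol*

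**What the plan says.** All references are to the prophylaxis synopsis in the protocol.

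- **Treatment time (Study design).** "Participants in the HCQ arm will take HCQ for 7 weeks only but will be monitored and evaluated up to study completion" at week 12, whereas "participants in the Ashwagandha arm will continue to take the drug for the total duration of 12 weeks". The same sentence adds for the Ashwagandha arm: "but will be monitored at 7th week, similar to those on HCQ".
- **Follow-up (Figure 1 and its notes).** "Participants will be monitored and followed using a common scheme shown above", and "HCQ will be given weekly for only 7 weeks (ICMR Advisory) but participants followed till study completion". Between visits there is "Daily Mobile App based feedback of any COVID-19 Symptoms or drug related side effects".
- **Outcomes (Efficacy criteria).** The secondary measures run "participants developing COVID-19, drug related adverse event", then drug tolerability and others. No window, denominator or exposure basis is attached to the safety items.
- **Collection (Safety criteria).** "All adverse events occurring during the study will be recorded and monitored as per GCP-ICH guidelines".
- **Analysis (Statistical statement).** Standard parametric and non-parametric tests, by intention to treat and per protocol, at two-sided p < 0.05.
- **Visits (Treatment and Follow up Monitoring Schedule, and the visit lists).** Baseline and weeks 4, 8 and 12. No week-7 visit is listed.

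**The concern.** Safety in comparison with HCQ is part of the stated objective, and drug-related events are a named secondary measure. From week 8 to week 12 one arm is on drug and the other is not. The trial is open label, so participants and assessors know that HCQ has stopped and are less likely to attribute a new symptom to it. A count of drug-related events to week 12 therefore covers up to 12 weeks on drug in one arm and 7 in the other.

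If two drugs had the same risk per week of use, the 12-week proportions would still differ. A reader who took those proportions as relative tolerability could conclude that Ashwagandha is the less well tolerated drug, or could miss a real advantage over HCQ. The primary efficacy endpoint is not affected.

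**Working it through.** **Inputs.** From the Study design text: 7 weeks on HCQ, 12 weeks on Ashwagandha, 12 weeks of follow-up in both arms, 400 participants in total. Assumed: 1:1 allocation (200 per arm; no ratio is stated) and all event rates and timings. The protocol gives no adverse-event rate and no safety calculation, so there is no stated figure to reproduce.

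**Step 1: planned weeks on drug.** HCQ 200 × 7 = 1400; Ashwagandha 200 × 12 = 2400. The ratio is 12/7 = 1.71.

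**Step 2: equal weekly risk r on drug, none after stopping.** The proportion with at least one drug-related event is 1 − (1 − r)^7 for HCQ and 1 − (1 − r)^12 for Ashwagandha.

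| r per week | HCQ | Ashwagandha | Ratio |
|---|---|---|---|
| 1% | 6.8% | 11.4% | 1.67 |
| 2% | 13.2% | 21.5% | 1.63 |
| 5% | 30.2% | 46.0% | 1.52 |

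**Step 3: what a plain two-sided 5% test would do.** Starting from a 7-week HCQ risk p7, the same weekly risk gives p12 = 1 − (1 − p7)^(12/7). The chance of a significant result against Ashwagandha is Φ[(p12 − p7 − 1.96 × SE0)/SE1], with SE0 pooled and SE1 unpooled. For p7 = 10%: p12 = 16.5%, SE0 = 0.0339, SE1 = 0.0338, and the chance is about 49%.

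| p7 | p12 | Ratio | Chance of a significant difference |
|---|---|---|---|
| 2% | 3.4% | 1.70 | 14% |
| 5% | 8.4% | 1.68 | 28% |
| 10% | 16.5% | 1.65 | 49% |
| 20% | 31.8% | 1.59 | 77% |
| 30% | 45.7% | 1.52 | 90% |

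The nominal rate is 5% in both directions together, so 2.5% in this one. On a common 7-week window, or per week on drug, the expected ratio under the same assumption is 1.00.

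**Step 4: sensitivity to timing.**

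- *Early clustering.* If a share s of Ashwagandha events falls by week 7, and the 7-week risk is 10% in both arms, the 12-week Ashwagandha risk is 10%/s. That is 13.3% at s = 75%, 11.1% at s = 90% and 10% at s = 100%. The ratios are 1.33, 1.11 and 1.00.
- *HCQ events after stopping.* If the HCQ risk continues unchanged for k weeks after week 7, the ratio of weeks at risk is 12/(7 + k): 1.71 at k = 0, 12/9 = 1.33 at k = 2 and 1.00 at k = 5.

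**Step 5: all adverse events.** With background rate b and drug-related rate d per week, the ratio of expected counts is (12b + 12d)/(12b + 7d). It is 1.16 for b = 2%, d = 1%; 1.26 for b = d = 1%; and 1.38 for b = 1%, d = 2%. Background events, collected equally in both arms, dilute the tilt.

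**The case against.** The strongest reply is that the protocol does not prescribe a plain 12-week comparison. It names the safety measures and refers to standard tests, which excludes neither a rate per person-time nor a 7-week cut. Such detail often sits in an analysis plan, and none is shown here. This stands: a reader might infer that the protocol commits the trial to a biased test, but the text does not support that. What the protocol does fix is the unequal treatment time, the single common window and a named safety measure without an exposure basis.

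Second, the collection sentence is sound. Following both arms to week 12 is needed to see late events after HCQ and events in the later Ashwagandha weeks. It would be wrong to infer that collection should stop at week 7.

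Third, five more weeks on drug may truly cause more drug-related events. That is a real property of the 12-week regimen, so the difference is not spurious as a description of the regimens. It misleads only when read as tolerability for equal use. This also stands.

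Fourth, the Study design text says the Ashwagandha arm is monitored at week 7 like the HCQ arm, which suggests that a matched look was intended. This is fair, but no week-7 visit is scheduled and no week-7 safety comparison is stated.

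Fifth, the size depends on a constant risk. The HCQ regimen described in the Background starts with a higher first day and continues weekly, which sits poorly with a constant weekly risk. The ratios of 1.5 to 1.7 are therefore near the upper end of the range.

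**Conclusion.** The point holds in limited form. Time on drug is 7 weeks against 12, and the safety measures have no exposure basis. Twelve-week totals of drug-related events therefore answer a question about the regimens, not about relative tolerability. Read as the latter, they tilt against Ashwagandha.

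The ratio is up to about 1.5 to 1.7, given an equal constant weekly risk on drug and no drug-related events after stopping. It falls towards 1 if events come early or HCQ-related events continue past week 7, and it is smaller for all adverse events. The protocol gives neither rates nor timing, so no single figure can be defended.

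A reader might infer that Ashwagandha is bound to look less safe, or that weeks 0-7 should be the only main safety comparison. The documents support neither. The tilt can vanish under plausible timing, and a 7-week comparison alone would hide Ashwagandha events in weeks 8-12 and late HCQ events.

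**What to change.** Add to the Statistical statement that drug-related and all adverse events will be compared between arms (a) by onset in weeks 0-7 and (b) as rates per person-week on drug, alongside (c) the full 12-week totals labelled with each arm's exposure. The 12-week totals keep Ashwagandha events in weeks 8-12 and late HCQ events visible. Onset dates must be recorded; the daily app feedback should make this possible with data already planned.

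Reconcile the statement that the Ashwagandha arm is monitored at week 7 with the visit schedule of weeks 4, 8 and 12, and say what that monitoring consists of.

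The cost is slightly more analysis and less precision in the matched window. The window leaves out 200 × 5 = 1000 of the 2400 planned Ashwagandha weeks on drug (42%, assuming 200 per arm). No change to treatment is implied.
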